5. PURPOSE AND STUDY OBJECTIVES

5.1 Purpose

The purpose of this study is to:

- Estimate the change in biomarkers of exposure (BOE) in adult smokers using VBM-FG2 versus adult smokers not using VBM-FG2.
- Determine the appropriate cigarettes per day (CPD) reporting method for baseline measurements (for interactive voice response system [IVRS] Base line is defined as the average CPD recorded on Days 2 through 8).

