Screening (Visit 1) will occur within 28 days of Day 1 (Day -28 to Day -1). An informed Consent Form (ICF) must be signed prior to conducting any study related procedures. Potential subjects will undergo an initial evaluation (vital signs, urine pregnancy test [females only], and questionnaires) to determine initial eligibility. If the subject passes the initial evaluation, then he/she will be provided with a sample of VBM-FG2 and asked to use the product as they like for 15 minutes. Subjects will then complete a Potential Purchase Interest Questionnaire. If they indicate that they "definitely would buy" or "probably would buy" the product on the questionnaire, then the subject will undergo the rest of the screening procedures (clinical labs and electrocardiogram [ECG]). Laboratory values will be evaluated by a local laboratory.

Subjects will return to the study site on the evening of Day 1 for Visit 2. A physical examination will be conducted and subjects who satisfy all the inclusion criteria and exclusion criteria will be eligible for enrollment in the study. Once a subject is enrolled in the study (Day 1), if they choose to no longer participate, they will be considered a drop-out/early termination subject.

During the Baseline Period, at Visits 2 and 3 (Days 1 and 8), blood and urine samples will be collected for analysis of BOE. Subjects will also complete the Past 7 Day Cigarettes Use Questionnaire while at the study site, to indicate their CPD over the previous week. During the Baseline Period (Days 1 to 8) subjects will report CPD daily through an IVRS.

At Visit 3, approximately 150 subjects will be randomized to either the Test or Control Group in a 3:2 ratio (with not more than a 60:40 distribution of either males or females to either group). VBM-FG2 will be dispensed to subjects randomized to the Test Group for *ad libitum* use beginning after the Day 8 IVRS.

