11.3.2 Secondary Endpoints

The secondary outcome measures or endpoints are:

- Differences in all BOE during the Baseline Period between Day 1 (weekly recall) versus Day 8 (daily tracking using IVRS).
- Difference in CPD during the Baseline Period between once weekly recall (Days 1 and 8) versus daily tracking (average of recordings on Days 2 through 8).
- Differences in the percent change from Baseline to EOS in BOE (urinary NE, S-PMA, blood COHb, exhaled CO) and CPD between the Test and Control Groups.
- Differences from Baseline to EOS in all BOE and CPD between the Test and Control Groups.
- Proporation of subjects in subgroups based on cigarette consumption change from Baseline to EOS (no change, <50% reduction, 50% reduction, 100% reduction, increase) within and between the Test and Control Groups.
- Proporation of subjects in subgroups based on total NNAL change from Baseline to EOS (no change, reduction, increase) within each group.
- Changes from Baseline (Day 8) to EOS in total scores of Fagerstrom Test for Cigarette Dependence (see Appendix 1), within and between the Test and Control Groups.
- Changes from Baseline (Day 1) to EOS on the Quit Attempts and Quitting Intentions, within and between the Test and Control Groups.

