11.4.1 Statistical Analyses of Primary Endpoint

A linear mixed model for repeated measures analysis of variance will be used for the analysis of the primary outcome measure. SAS procedure Proc Mixed will be used for the statistical computing. The null hypothesis is that smokers allowed *ad libitum* use of VBM-FG2 discs (test) will not differ in the primary biomarker (percent change from baseline to EOS in urinary total

NNAL) compared to smokers not allowed use of VBM-FG2 discs (control). The alternative hypothesis is that smokers allowed *ad libitum* use of VBM-FG2 discs will differ in the primary biomarker compared to smokers not allowed use of VBM-FG2 discs. The model will include percent (or absolute) change from baseline to EOS in urinary total NNAL as a response variable, product, visit, and product by visit interaction as fixed effects; and subject as random effect. In the expanded model, several additional factors will be considered. Details about the models are as follows:

Model 1:

Percent (or absolute) change from baseline in total NNAL = study group + visit + study group*visit + subject + random error

Model 2:

Percent (or absolute) change from baseline in total NNAL = study group + visit + study group*visit + subject + CPD + sex + race + body mass index (BMI) + age + random error

where

CPD = fixed covariate representing average number of cigarettes per day for past week from IVRS

study group = fixed effect term (test or control)

sex = fixed effect (male or female)

race = fixed effect (White or Non-White)

BMI = fixed effect covariate

age = fixed effect covariate (continuous)

visit = fixed effect term representing days (ordinal categorical variable)

subject = random subject effect

baseline = Total NNAL measure at Day 8

If the study group*visit interaction term is not statistically significant (P-value > 0.10), then the interaction term will be removed from the model and all comparisons will be done using the overall product means. If the interaction effect is significant (P-value < 0.10), then the comparisons will be conducted for each study visit. Comparisons between products will be done based on 5% level of significance.

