11.4.2 Statistical Analyses of Secondary Endpoints

Difference in baseline:

Paired T Test will be used to examine the difference in all 5 BOEs between Day 1 and Day 8.

Paired T test will also be used to examine the differences in CPD between the once weekly recall at Day 8 (from questionnaire) and the average daily tracking of CPD from Days 2 through 8 (from IVRS).

Difference in change from baseline:

Linear mixed model for repeated measures analyses of variance will be used for the analyses of the secondary outcome measures: percent change from baseline and absolute change from baseline in all other BOEs. The same model will be used for percent change from baseline and absolute change from baseline in CPD and Total score of FTCD, the model details are as follows:

For other BOEs:

Model 1:

Percent (or absolute) change from baseline = study group + visit+ study group*visit + subject + random error

Model 2:

Percent (or absolute) change from baseline = study group+ visit+ study group*visit + subject + CPD + sex + race + BMI + age + random error

For CPD and Total Score ofFTCD:

Model 1:

Percent (or absolute) change from baseline = study group+ visit+ study group*visit +subject+ random error

Model 2:

Percent (or absolute) change from baseline = study group+ visit+ study group*visit +subject+ sex + race + BMI + age + random error

where

CPD = fixed effect covariate representing average number of cigarettes per day for the past two days from IVRS

study group = fixed effect term (test or control)

sex = fixed effect (male or female)

age = fixed effect covariate (continuous)

race= fixed effect (White or Non-White)

BMI = fixed effect covariate (continuous)

visit= fixed effect term representing days (ordinal categorical variable)

subject = random effect

baseline = Day 8 value for BOE and average of Day 2 to 8 for CPD (IVRS)

If the study group*visit interaction term is not statistically significant (P-value > 0.10), then the interaction term will be removed from the model and all comparisons will be done using the overall product means. If the interaction effect is significant (P-value < 0.10), then the comparisons will be conducted for each study visit.

Least squared mean and standard error for the product effect will be estimated by study group and visit with p-values for statistical significance. P-value will also be provided for other effects in the model.

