All secondary and exploratory analyses will be conducted on the Per-protocol population only.

A linear regression analysis will be conducted within each group at each timepoint to examine the relationships between levels of all 5 BOEs (dependent variable) with either weekly cigarette counts (Day 1 and 8 from questionnaire) or daily cigarette counts (from IVRS) (independent variable). For total NNAL, the corresponding daily cigarette counts from IVRS will be the average of past 7 days. For other biomarkers, it will be the average of past 2 days. The regression analysis will be conducted on the Per-protocol population.

The proportion of subjects in subgroups will be provided with proportion and sample size based on:

- 1) Cigarette consumption change from Baseline (average of Days 2 to 8 from IVRS) to the last week (no change, <50% reduction, 2::50% reduction , 100% reduction, increase);
- 2) Total NNAL change from Day 8 to the last visit (no change, reduction, increase);
- 3) Total scores of FTCD change from Day 8 to the last visit (increase, no change, decrease)
- 4) Proportion of subjects in subgroups based on Changes from Baseline (Day 1) to EOS (increase, no change, decrease) on the change in Quit Attempts from Day 1 to last visit.
- 5) Proportion of subjects in subgroups based on Changes from Baseline (Day 1) to EOS (yes to no, no to yes, and same) on the change in Quitting Intentions from Day 1 to last visit.

The Mantel-Haenszel Chi-Square Test will be used for (1), (2), (3), and (4); Fisher exact test will be used for (5) to test the frequency differences between the two groups.

Additional statistical analyses:

Wilcoxon signed rank test will be used to test the FTCD score difference between the 2 baseline measures (Visit 2 and 3) for the test group. If there is no statistical significance, the average score will be related to the average amount of VBM-FG2 in the past week via linear regression. Otherwise the FTCD score for Visit 3 will be used.

For the test group only, a simple linear regression model will be used to examine the relationship between COHb and Exhaled CO at each post-baseline visit.

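### The direct comparison of recall and IVRS CPD tests mean bias only, although one stated purpose is to choose between the two reporting methods

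*SAP*

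**What the plan says.** SAP Section 5.1 gives two purposes. The second is to "Determine the appropriate cigarettes per day (CPD) reporting method for baseline measurements".

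Section 11.3.2 turns this into a secondary endpoint: "Difference in CPD during the Baseline Period between once weekly recall (Days 1 and 8) versus daily tracking", the daily tracking being the IVRS average over Days 2 to 8.

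Section 11.4.2 (Difference in baseline) gives the test: "Paired T test will also be used to examine the differences in CPD between the once weekly recall at Day 8 (from questionnaire", compared with the same IVRS average. It names no agreement measure, no acceptable difference in CPD, and no rule for choosing a method from the result.

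The two measures appear together in one other planned analysis. Within each group and at each timepoint, the levels of the five biomarkers are regressed on CPD, "with either weekly cigarette counts (Day 1 and 8 from questionnaire) or daily cigarette counts (from IVRS) (independent variable". For total NNAL the IVRS value is a 7-day average; for the other four biomarkers it is a 2-day average.

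On population, the same section says: "All secondary and exploratory analyses will be conducted on the Per-protocol population only".

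**The concern.** Choosing between two ways of measuring the same quantity in the same person is a question about agreement. Two methods can have equal means and still give very different values for many individuals. That matters because baseline CPD is used one subject at a time: each subject has an individual percent change (Section 11.1) and is placed in a reduction class (Section 11.4.2). Errors that cancel in the group mean do not cancel there.

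The paired t test covers one part of the question, systematic bias. Scatter in the differences enters it only through the standard error and is never itself the result. If the method conclusion rests on this test, close agreement and very poor agreement can look the same. At stake is the advice that this pilot gives about baseline CPD in later work.

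**Working it through.** The SAP states no SD, power, margin or agreement criterion for this comparison, and Section 8 contains no calculation, so there is no figure to reproduce. What follows is an illustration.

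**Inputs**
- Pairs: "At Visit 3, approximately 150 subjects will be randomized to either the Test or Control Group in a 3:2 ratio" (Section 6). Because the analysis is Per-protocol, 150 is an upper bound. The Per-protocol number is not given; 100 to 150 is assumed.
- Significance level: "Comparisons between products will be done based on 5% level of significance" (Section 11.4.1) refers to product comparisons. Two-sided 5% is assumed for the paired t test too.
- SD of the within-subject difference d = recall − IVRS: not in the SAP. Assumed values are 2, 5, 8 and 10 CPD, with d normally distributed.

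**Formulas**
- 95% CI half-width of the mean difference: t(0.975, n−1) × SD/√n
- 95% limits of agreement: mean d ± 1.96 × SD
- Share differing by more than 5 CPD at zero mean bias: 2 × [1 − Φ(5/SD)]
- Rejection rate: noncentral t with noncentrality bias/(SD/√n)

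**Results at n = 150**

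| SD of d | CI half-width of mean | Limits (zero bias) | Differ by >5 CPD | Rejection, zero bias | Rejection, bias 1 CPD |
|---|---|---|---|---|---|
| 2 | 0.32 | ±3.9 | 1% | 5% | about 100% |
| 5 | 0.81 | ±9.8 | 32% | 5% | 68% |
| 8 | 1.29 | ±15.7 | 53% | 5% | 33% |
| 10 | 1.61 | ±19.6 | 62% | 5% | 23% |

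Example for SD 8: 1.96 × 8 = 15.7; 5/8 = 0.625, and 2 × [1 − Φ(0.625)] = 0.53.

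At n = 100 the limits, the shares and the 5% are unchanged. Rejection with a 1-CPD bias becomes 99.9%, 51%, 24% and 17%.

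**Three readings of the table**
1. With zero bias, the rejection rate is the same in every row although agreement ranges from close to very poor. The test cannot tell the rows apart; the limits can.
2. With a real 1-CPD bias, more scatter makes a non-significant result more likely.
3. At SD 2 a 1-CPD bias is almost always significant, although about 95% of subjects lie within 3.9 CPD of that bias.

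**Extreme case.** In 20,000 simulated trials every subject's two reports differed by exactly 8 CPD, with random sign. The paired t test was significant in 5.8% (n = 100) and 6.0% (n = 150).

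**The case against.** **The regressions already examine both methods.** They relate each CPD measure to an outside marker of exposure, which agreement statistics cannot do. Random recall error would also show there as a weaker slope. If CPD has a between-subject SD of 6 (an assumption) and all disagreement is recall error, the recall slope shrinks by the factor 6²/(6² + SD²): 0.90 at SD 2, 0.59 at SD 5, 0.36 at SD 8. This stands, so the paired t test is the only direct comparison but not the only relevant evidence. It does not close the gap. No comparison of the two fits is planned, within-subject agreement is not estimated, and for four of the five biomarkers the IVRS value covers two days while recall covers a week, which mixes method with time window.

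**The SAP never says that P>0.05 means the methods are interchangeable.** Correct; a reader might infer such a rule, but none is written. The reading is still foreseeable, because no other criterion is given. In the same section, a non-significant Wilcoxon test between the two baseline FTCD measures in the Test Group leads to their average being used.

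**No result of this trial depends on it.** Largely correct. Section 11.2 fixes the CPD baseline to the IVRS average, the reduction classes use it too, and the Model 2 CPD covariate also comes from IVRS.

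**The scatter may be tabulated anyway.** Section 11.1 lists the SD among its general summaries, and the TFL shells are not shown. But the SAP does not specify it for the recall-minus-IVRS difference or tie it to the method conclusion.

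**Conclusion.** The point holds in a limited form. The direct comparison addresses mean bias, while the stated purpose needs within-subject agreement as well. In the illustration, a difference SD of 2 CPD and one of 8 CPD give the same 5% rejection rate at zero bias, although 1% and 53% of subjects respectively differ by more than 5 CPD. The SDs are assumptions. If the true SD is near 2, adding limits of agreement would change little.

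A reader might go further and infer that noisier recall always makes non-significance more likely, so that the test favours the worse method. The calculation does not support that: at zero bias the rate stays at 5% whatever the scatter, and noise matters only when a real bias exists. Nor do the documents support a claim that this trial's own CPD results are compromised.

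What is affected is the conclusion about reporting method. Sections 6, 8 and 12 tie this pilot to a planned pivotal study but do not say how the choice of CPD method will be used there; that it will be carried forward is an inference from Section 5.1. The change is worth making and does not touch the primary endpoint.

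**What to change.** In SAP Section 11.4.2 (Difference in baseline):
- Keep the mean difference and report it with its 95% CI.
- Add Bland-Altman 95% limits of agreement with CIs, and a plot of difference against mean, for Day 8 recall against the IVRS average over Days 2 to 8.
- Have the sponsor state in advance what difference in CPD is acceptable, and judge the limits against it. Without this the limits describe but do not decide.
- Say that the limits will be read alongside the biomarker regressions.
- State that P>0.05 on the paired t test will not be read as agreement.

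Two points to settle in the same edit. Section 5.3 names Day 1 recall, Section 11.3.2 names Days 1 and 8, and Section 11.4.2 tests Day 8 only; these should be reconciled. Day 8 recall covers about the same week as the IVRS average, but it follows a week of daily reporting and may agree better than untracked recall would. The report should say so.

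**Cost.** SAP wording plus one table and one figure, from data already collected. The limits are estimates: the 95% CI half-width of each is about 1.96 × √3 × SD/√n. At n = 150 that is 0.55 CPD for SD 2 and 2.2 for SD 8; at n = 100 it is 0.68 and 2.7.

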5.3 Secondary Objectives

The secondary objectives of this study are to:

- Compare the difference in BOE (urinary total NNAL, nicotine metabolites, S-phenylmercaptmic acid [S-PMA], blood carboxyhemoglobin [COHb], and exhaled carbon monoxide [CO]) and CPD between two methods for determining CPD during the Baseline Period:
 - Recall of average daily CPD for prior week using Past 7 Day Cigarettes Use Questionnaire (Day I).
 - Daily CPD tracking using an IVRS (7 day average of values recorded on Days 2 through 8).
- Compare the differences in percent change in urinary nicotine equivalent (NE), S-PMA, blood COHb, exhaled CO, and CPD from Baseline to EOS between adult smokers randomly assigned to Test Group (*ad libitum* VBM-FG2 use) and Control Group (no VBM-FG2).
- Compare the changes in all BOE and CPD from Baseline to EOS between Test Group and Control Group over 4 weeks.
- Characterize subgroups based on change in CPD from Baseline to EOS (no change, <50% reduction, ≥50% reduction, 100% reduction, increase) within each study group.
- Characterize subgroups based on change in total NNAL from Baseline to EOS (no change, reduction, increase) within each study group.
- Compare changes in the Fagerstrom Test for Cigarette Dependence (FTCD) from Baseline (Day 8) to EOS within and between each study group.
- Compare changes on the Quit Attempts and Quitting Intentions from Baseline (Day I) to EOS within and between each study group.

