11.2 Definition of Baseline for Calculating Change

The Baseline Period is from Day 1 to Day 8. The baseline for calculating change from baseline will be defined in the following table.

Metric	Baseline	Corresponding post-baseline visits
Quit Attempts and Quitting Intentions	Day 1 (Visit 2)	Day 36 (Visit 7)
Fagerstrom Test for Cigarette Dependence (FTCD)	Day 8 (Visit 3)	Day 36 (Visit 7)
BOE	Day 8 (Visit 3)	Visits 4, 5, 6, 7
CPD daily tracking from IVRS	The average of available data from Day 2 through Day 8	Daily CPD Day 9 to 36 or the average of last week at Visits 4, 5, 6, 7
Vital Signs	Day 8, including unscheduled (rechecked) values	Visits 4, 5, 6, 7
*see Section 11.4.3 for more details		

Rationale for the baseline choices for calculating change:

Quit attempts and intentions: Day 1 is the only one measurement in baseline.

FTCD: There are 2 measurements in the baseline, Day 1 and 8. Day 8 is selected because it is anticipated that there will be changes in CPD, a key component of the FTCD score, when adult smokers are asked to track their daily cigarette consumption. Day 1 value does not reflect this change.

BOE: Day 8 is the last of the 2 baseline values and is closer to the post-baseline values.

CPD daily tracking: The weekly average was selected to adjust for the daily variability and also because total NNAL (primary end-point) has a longer half-life and the average CPD might be better representative of changes in exposure to total NNAL than the individual values.

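### For CPD, the objective and endpoint name Day 1 recall versus IVRS, but the planned paired test uses Day 8 recall only, so the Day 1 contrast is left untested

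*SAP*

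**What the plan says.** SAP Section 5.1 gives as one of two purposes: "Determine the appropriate cigarettes per day (CPD) reporting method for baseline measurements". Section 5.3 turns this into a secondary objective, which compares biomarkers of exposure (BOE) "and CPD between two methods for determining CPD during the Baseline Period". It defines the two methods as:

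- "Recall of average daily CPD for prior week using Past 7 Day Cigarettes Use Questionnaire (Day I"), that is, the questionnaire on Day 1 only;
- "Daily CPD tracking using an IVRS (7 day average of values recorded on Days 2 through 8").

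Section 11.3.2 makes the CPD endpoint wider, as "once weekly recall (Days 1 and 8) versus daily tracking (average of recordings on Days 2 through 8"). Section 11.4.2, under the baseline differences, then plans one paired t test for CPD. Its recall side is "the once weekly recall at Day 8 (from questionnaire") and its other side is the IVRS average of Days 2 to 8. The sentence before it plans paired t tests of all five BOEs between Day 1 and Day 8.

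Section 6 has subjects complete the recall questionnaire at both Visit 2 (Day 1) and Visit 3 (Day 8), and report CPD by IVRS each day of the Baseline Period. Section 11.2, in explaining why the Day 8 FTCD score is the baseline, expects CPD to change "when adult smokers are asked to track their daily cigarette consumption" and notes that the Day 1 value does not carry that change.

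**The concern.** The objective, the endpoint and the analysis name three different sets of recall days for the same CPD comparison. The recall day on which the objective rests, Day 1, is the one missing from the test.

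The days are not interchangeable. Day 1 recall is taken before daily reporting has had time to act and describes the week before the Baseline Period. Day 8 recall is taken after a week of daily reporting and describes about the same week as the IVRS average. An analyst who follows Section 11.4.2 to the letter would report on the reporting-method purpose without the contrast that Section 5.3 specifies. A reader who compares the report with the objective could take the Day 8 result as the answer to the Day 1 question. This is a pilot meant to inform a later pivotal study, so the choice of CPD method is one of the things it is expected to deliver.

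**Working it through.** The plan states no figure for this comparison, so there is nothing to recompute. The check follows the comparison through the SAP and then asks what each contrast measures.

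**Step 1. Trace**

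| SAP section | CPD: recall day set against IVRS Days 2 to 8 | BOE contrast |
|---|---|---|
| 5.3 Objective | Day 1 | between the same two methods |
| 11.3.2 Endpoint | Days 1 and 8 | Day 1 versus Day 8 |
| 11.4.2 Planned test | Day 8 only | Day 1 versus Day 8 |

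The BOE column is consistent from endpoint to test. The CPD column is not: of the two contrasts listed in Section 11.3.2, one is tested and one is not.

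**Step 2. Is Day 1 recall CPD tested anywhere else?**

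The SAP gives it one other use. Section 11.4.2 regresses BOE levels on questionnaire counts (Days 1 and 8) or on IVRS counts. This bears on which CPD measure tracks exposure better, and so on the purpose in Section 5.1. It does not estimate a difference in CPD between methods. Planned tests of Day 1 recall CPD against IVRS CPD: 0.

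**Step 3. What each contrast measures**

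For one subject, let T0 be true CPD in the week before Day 1 and T1 true CPD in the baseline week. Let e1 and e8 be the recall errors on Days 1 and 8, and i the error of the IVRS average. Then:

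- Day 1 recall: R1 = T0 + e1
- Day 8 recall: R8 = T1 + e8 (about the same week as the IVRS average)
- IVRS average: I = T1 + i

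The contrasts are:

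- R8 − I = e8 − i. This is a difference between methods; real change in smoking cancels.
- R1 − I = (T0 − T1) + (e1 − i). This is real change plus a difference between methods.
- (R1 − I) − (R8 − I) = R1 − R8 = (T0 − T1) + (e1 − e8). This is the same instrument before and after tracking.

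The planned test estimates the first quantity. The objective names the second. If tracking changes smoking, as Section 11.2 anticipates, T0 − T1 is not zero, and the two contrasts differ even when both instruments are accurate. Neither can stand in for the other.

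**Step 4. Are the data there?**

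Yes. Section 6 has the questionnaire completed at Visits 2 and 3 and CPD reported daily by IVRS, so the missing contrast needs no new collection.

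**The case against.** The strongest reply is that the planned test is the better method comparison. Day 8 recall and the IVRS average cover about the same week, so their difference reflects the methods. A Day 1 comparison would bring in real behaviour change and could show a difference even if both methods were accurate. This stands. It is a reason to keep the Day 8 test and not to make the Day 1 contrast the sole test of the objective. It does not explain why a contrast named in both Section 5.3 and Section 11.3.2 has no analysis.

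It is also fair to say that the gap is narrow. Section 11.2 already fixes baseline CPD as the IVRS average, so no change-from-baseline analysis in this trial depends on the missing test. The final TFL shells are a separate document and are not shown, so a descriptive Day 1 table may exist; the SAP text specifies no test.

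Three stronger readings may tempt a reader, and the SAP does not support them.

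- *The objective's comparison is never made.* This is too broad. The BOE half is tested Day 1 versus Day 8, and the Day 8 part of the CPD endpoint is tested too.
- *Day 8 recall is primed by a week of reporting, so the planned test overstates agreement.* Priming is plausible, but nothing in the SAP shows it or its size. Section 11.2 anticipates a change in CPD, not an error in recall, and gives no direction.
- *Only Day 1 recall versus IVRS could show an effect of tracking.* This is not so. The BOE tests of Day 1 against Day 8 are a before-and-after contrast. The FTCD comparison of Visits 2 and 3, in the Test Group, is another, and CPD is one of its items. Day 1 against Day 8 recall would also show such an effect, with one instrument.

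**Conclusion.** The inconsistency is real and limited to CPD. The objective names Day 1 recall, the endpoint names Days 1 and 8, and the test uses Day 8 only. One of the two named CPD contrasts therefore goes untested, for a secondary objective that serves one of the study's two purposes. The primary endpoint, the BOE half of the objective and the definition of baseline CPD are not affected.

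The finding rests on the wording of Sections 5.3, 11.3.2 and 11.4.2 alone. It needs no assumption about the size or direction of any tracking effect, the spread of CPD differences or the accuracy of recall. The SAP gives none of these, so no power or bias figure is attached. Section 13 reports no changes from the protocol's analyses. The protocol is not at hand, so whether the mismatch began there cannot be said.

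The plan should be corrected, but the correction is modest.

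**What to change.** In Section 11.4.2, under the baseline differences:

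1. Add a paired comparison of Day 1 recall CPD with the IVRS average of Days 2 to 8, reported as a mean difference with its 95% CI.
2. Keep the Day 8 recall versus IVRS comparison, and label it as the check of agreement between methods over about the same week, after daily tracking.
3. State that the Day 1 comparison covers an earlier, untracked week, so that it includes any real change in smoking as well as the difference between methods and is not a pure test of method.
4. Align Sections 5.3, 11.3.2 and 11.4.2 so that all three name the same recall days and say which question each contrast answers.

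The cost is one more paired analysis on data already collected, in the Per-protocol population that Section 11.4.2 sets for all secondary analyses, plus edits to the wording of three sections. No change to visits, sample size or the primary analysis is needed.
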